6.2.1 Adverse Event Assessments

See also Section [9.4](#) and [Appendix 1](#).

For those subjects who receive a dose of ARCT-021 in this study:

Local and systemic solicited and unsolicited AEs will be recorded daily by the subject in a symptom diary for at least 7 days post injection and up to 14 days post injection if any events are persisting at 7 days. Subjects will record their temperature daily in the symptom diary during these 7 days. Additionally, any injection site erythema or swelling will be measured in the longest dimension and recorded in the symptom diary.

Unsolicited adverse events will be collected at each study visit from post injection on Day 1 throughout the participation of the subject in the study; however, after a subject reaches Day 29 of study participation only the unsolicited AEs defined as MAAEs, SAEs, CESIs, NOCDs will be summarized. Unsolicited adverse events will be determined from reporting of these events in the diary card, review of clinical laboratory values, performance of physical exam, and interview of the subject.

The symptom diaries will be reviewed by site staff at the Day 8 (and Day 15 if subject completing diary for an additional 7 days) visit for the first injection and at the Day 36 (and Day 43 if subject completing diary for an additional 7 days) visit for the second injection. Subjects will be specifically questioned about injection site and systemic (fever, fatigue, headache, chills, nausea, vomiting, diarrhoea, new or worsened myalgia, and new or worsened arthralgia) at these visits.

Should a solicited AE persist beyond 14 days post injection (past Day 15 for the first injection or Day 43, if second injection), this will be followed by interview and/or physical examinations at follow-up visits until resolution or stabilization.

Study site staff will enter the temperature and erythema/swelling dimension measurements recorded in the symptom diary into the EDC. Subjects grading of reactogenic events, as recorded in the symptom diary, will be entered in the EDC without change. Any unsolicited events recorded by the subject in the symptom diary will be entered verbatim into the EDC.

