Any recorded temperature $\geq 38^{\circ}\text{Celsius}$ ($\geq 100.4^{\circ}\text{ Fahrenheit}$) or injection site erythema/swelling $\geq 25\text{mm}$ in size will be reported as an adverse event and graded according to Toxicity Grading Scale for Healthy Adult and Adolescent Volunteers Enrolled in Preventive Vaccine Clinical Trials, Sept 2007.

Solicited events with onset within 7 days of injection will be considered related.

Symptom diaries will be collected at the Day 8 or 15 (depending on completion status) visits for the first injection and 36 or 43 visits for the second injection and will serve as source documents.

For those subjects who received ARCT-021 in the Parent Study:

At Screening, SAEs, NOCDs, CESIs and MAAEs occurring between completion of the Parent Study and the Screening visit for this study will be solicited and recorded in the EDC to ensure continuity of safety follow-up from the Parent Study to this study. Events that occurred prior to dosing in this study will be recorded as medical history.

For subjects who received ARCT-021 in either the Parent Study or this study:

SAEs, NOCDs, CESIs, and MAAEs will be collected for all enrolled subjects for the duration of the study until the Final Visit (Day 365 or Day 281 if vaccinated or not vaccinated with ARCT-021 in this study) or Early Termination visit (if applicable).

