***Subjects that terminate early should complete all procedures for Study Day 281**

- 1 Abbreviated physical exam (assessment of vitals, heart, lungs, lymphatic, abdomen and symptom directed examination, if any symptoms) to be given during observation period to assess changes from screening.
- 2 BP, HR, RR, temp
- 3 Stored at -70 °C for follow up immunological assessments or exploration of laboratory findings and/or adverse events
- 4 SAE, CESI, NOCD and MAAEs will be recorded.
- 5 At each visit, subjects will be questioned about symptoms of COVID-19 and exposure to confirmed COVID-19 or confirmed SARS-CoV-2 infection cases amongst household contacts, friends, work contacts and other contacts.
- 6 Subjects that terminate from the study before completion will be told to inform the study site staff if they develop symptoms compatible with COVID-19 (Section 6.2.4) or a diagnosis of SARS-CoV-2 infection or COVID-19 for one year after vaccination so that they can be adequately followed up.

Subjects Receiving a Single Injection of ARCT-021 in This Study

Study Week/Day	Study Drug Administration	Post-Treatment Period (52 Weeks)							
		W1 D1	W2 D8	W3 D15	W5 D29	W9 D57	W25 D169	W37 D253	W53 D365/ Early Term*
Visit Window (Days)	0	±1	±1	0	±7	±14	±14	+14	
Physical Exam ¹	X ^a	X	X	X	X	X	X	X	X
Vital Signs ²	X ^a	X	X	X	X	X	X	X	X
Pregnancy Test ³	X ^a								
Chemistry Panel	X ^a	X	X	X					
Hematology	X ^a	X	X	X					
Coagulation	X								
HbA1c	X								
Urinalysis ⁴	X ^a	X		X					
Archived plasma sample ⁵	X ^a			X	X	X	X	X	X
Archived serum sample ⁵	X ^a			X	X	X	X	X	X
Archived PBMC sample ⁵	X ^a		X	X	X	X	X	X	X
Immunogenicity	X ^a			X	X	X			X
T-cell responses	X ^a		X	X		X			X
Drug/Alcohol Screen ⁶	X ^a								
Study Drug Administration	X								
Review of symptom diary ⁷		X	X						
Unsolicited AE	X	X	X	X					
SAE, CESI, NOCD and MAAE ⁸	X	X	X	X	X	X	X	X	X
Concomitant Medications and Procedures	X	X	X	X					
SARS-CoV-2 questioning ⁹	X	X	X	X	X	X	X	X	
Counselling about long-term follow-up for SARS-CoV-2 infection ¹⁰									X

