***Subjects that terminate early should complete all procedures for Study Day 365**

- 1 Full physical exam to be given at Day 1 and Day 365/Early Termination; abbreviated physical exam (assessment of vitals, heart, lungs, lymphatic, abdomen and symptom directed examination, if any symptoms) to be given during treatment and follow-up period to assess changes from screening. Injection site to be inspected at all visits after injection until resolution of local reactogenicity event(s).
- 2 BP, HR, RR, temp
- 3 Women who are not surgically sterile or post-menopausal. Dipstick acceptable
- 4 Dipstick test per local procedures. If abnormal send sample to laboratory for microscopy.
- 5 Stored at -70 °C for follow up immunological assessments or exploration of laboratory findings and/or adverse events
- 6 Can be done at the site using established methods, e.g., a breathalyzer or urine test.

- 7 Symptom diary to be reviewed on Day 8. If subject has any unresolved local or systemic reactogenic events then they should be instructed to continue to complete the symptom diary for a further week and the symptom diary should be reviewed again at Day 15. This review includes specifically asking about injection site and systemic (fever, fatigue, headache, chills, nausea, vomiting, diarrhoea, new or worsened myalgia, and new or worsened arthralgia) events. If not being completed for the second week after injection, then the symptom diary will be collected on Day 8; otherwise symptom diary to be collected on Day 15.
- 8 Only SAE, CESI, NOCD and MAAE will continue to be recorded after Day 29.
- 9 At each visit, subjects will be questioned about symptoms of COVID-19 and exposure to confirmed COVID-19 or confirmed SARS-CoV-2 infection cases amongst household contacts, friends, work contacts and other contacts.
- 10 Subjects that terminate from the study before completion will be told to inform the study site staff if they develop symptoms compatible with COVID-19 (Section 6.2.4), or a diagnosis of SARS-CoV-2 infection or COVID-19 for one year after vaccination so that they can be adequately followed up.

Time (time is in reference to Study Drug administration):

a Pre-dose

If not specifically labeled, "X" means anytime

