- ii. the number and percentage of participants experiencing a solicited event by Systemic vs Local and by event term, day post vaccination (from Day 1 to Day 7, where Day 1 is the day of injection), by age groups, and the maximal severity. The number and percentage of participants experiencing a solicited event, by event term, by age group, occurring at any time from Day 1 to Day 7 will also be displayed.

The age groups referenced above are all participants, 21 to 55 years, and 56 to 80 years at the time of enrollment in the Parent Study. Cohort/sub-cohorts are described in Section [5.2](#).

8.1.9.3 Adverse Events After Off-Study Vaccine.

- i. An overall summary of unsolicited treatment emergent adverse events with onset after injection of off-study vaccine, longitudinal Safety population which includes, by age group:
 - a. the number and percentage of participants experiencing an AE leading to study withdrawal
 - b. the number and percentage of participants experiencing a SAE by maximal severity
 - c. the number and percentage of participants experiencing an MAAE
 - d. the number and percentage of participants experiencing a NOCD

The age groups referenced above are all participants, 21 to 55 years, and 56 to 80 years at the time of enrolment in the Parent Study.

NOTE: unsolicited AE that are not SAE, MAAE or NOCD are not collected in this study for participants in cohort 2 and are only collected up to 28 days after injection of ARCT-021 for participants in cohorts 1a and 1b. No participants received an off-study vaccine within the time window for collection of unsolicited AE that are not SAE, MAAE or NOCD, so no tabulation of all unsolicited events is being provided.

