Assessment after Screening Period

Participants Not receiving ARCT-021 in This Study.

Study Week/Day	Observation Period (40 Weeks)				
	W1 D1	W5 D29	W13 D85	W29 D197	W41 D281/or Early Term*
Visit Window (Days)	0	± 7	± 7	± 14	± 14
Physical Exam ¹	X		X	X	X
Vital Sign ²	X		X	X	X
Archived plasma sample ³	X	X	X	X	X
Archived serum sample ³	X	X	X	X	X
Archived PBMC sample ³	X	X	X	X	X
Immunogenicity		X		X	X
T-cell response		X		X	X
SAE, CESI, NOCD and MAAE ⁴	X	X	X	X	X
SARS-CoV-2 questioning ⁵	X	X	X	X	X
Counselling about long term follow-up for SARS-CoV-2 infection ⁶					X

* Participants that terminate early should complete all procedures for Study Day 281

1 Abbreviated physical exam (assessment of vitals, heart, lungs, lymphatic, abdomen and symptoms directed examination, if any symptom) to be given during observation period to assess changes from screening.

2 BP, HR RR, temp.

3 Stored at -70°C for follow up immunological assessment or exploration of laboratory findings and/or adverse events.

4 SAE, CESI, NOCD and MAAE will be recorded.

5 At each visit participants will be questioned about symptoms of COVID-19 and exposure to confirmed COVID-19 or confirmed SARS-COV-2 infection cases amongst household contacts, friends, work contacts and other contacts.

6 Participants that terminate from the study before completion will be told to inform the study site staff if they develop symptoms compatible with COVID-19 (Section 6.2.4), or a diagnosis of SARS-CoV-2 infection or COVID-19 for one year after vaccination so that they can be adequately followed up.

Participants Receiving a Single Injection of ARCT-021 in This Study.

Study Week/Day	Study vaccine Administration	Post-Treatment Period (52 Weeks)						
		W2 D8	W3 D15	W5 D29	W9 D57	W25 D169	W37 D253	W53 D365/ Early Term*
Visit Window (Days)	0	±1	±1	0	±7	±14	±14	±14
Physical Exam ¹	X ^a	X	X	X	X	X	X	X
Vital Sign ²	X ^a	X	X	X	X	X	X	X
Pregnancy Test ³	X ^a							
Chemistry Panel	X ^a	X	X	X				
Hematology	X ^a	X	X	X				
Coagulation	X ^a							
HbA1c	X ^a							
Urinalysis ⁴	X ^a	X		X				
Archived plasma sample ⁵	X ^a			X	X	X	X	X
Archived serum sample ⁵	X ^a			X	X	X	X	X
Archived PBMC sample ⁵	X ^a		X	X	X	X	X	X
Immunogenicity	X ^a			X	X	X		X
T-cell responses	X ^a		X	X		X		X
Drug/Alcohol Screen ⁶	X ^a							
Study vaccine Administration	X							
Review of symptom Diary ⁷		X	X					
Unsolicited AE	X	X	X	X				
SAE, CESI, NOCD and MAAE ⁸	X	X	X	X	X	X	X	X
Concomitant Medications and Procedures	X	X	X	X				

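### The Day 8 visit window lets the symptom diary be collected on Day 7, so the 7-day record behind the primary reactogenicity endpoint is not guaranteed complete

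*Protocol*

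**What the plan says.** Protocol 6.2.1 has subjects who are dosed in this study record events daily, and sets the duration as follows: "symptom diary for at least 7 days post injection and up to 14 days post injection if any events are persisting at 7 days". The same section says: "Symptom diaries will be collected at the Day 8 or 15 (depending on completion status) visits". Footnote 7 of the single-injection schedule in Appendix 1 repeats the rule: "If not being completed for the second week after injection, then the symptom diary will be collected on Day 8". Subjects with any unresolved reactogenic event at the review keep the diary for another week, and it is reviewed again at Day 15.

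The window row of that schedule reads "Visit Window (Days) 0 ±1 ±1 0 ±7 ±14 ±14 +14". The second entry belongs to Day 8. The SAP copy in Appendix A differs only in the last column: "Visit Window (Days) 0 ±1 ±1 0 ±7 ±14 ±14 ±14".

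Protocol 10.5.3 lists solicited events over the 7 days after vaccination (Cohort 1) among the primary safety endpoints. SAP 8.1.9.2 plans two outputs. Table (i) counts events with onset up to and including 7 days after injection. Table (ii) shows events by "day post vaccination (from Day 1 to Day 7, where Day 1 is the day of injection". SAP 5.4 says that missing data are not imputed. No denominator is stated for the by-day solicited table.

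**The concern.** The recording period is a fixed number of days, but collection is tied to a visit that may come a day early. A site can follow every printed rule and still take the diary before the required period has ended. The subjects whose diaries are taken early are those with nothing unresolved at the visit, so what can be lost is a new event starting later that day.

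Solicited events are part of the primary endpoint, and the diary is their source document. The plan also does not say how a day without an entry is treated. A gap in recording could therefore appear in the by-day table as absence of an event.

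**Working it through.** The documents give no rate or sample size that bears on this point, so there is no plan figure to reproduce. The check is day arithmetic followed by an illustration on assumed values.

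**1. Complete days at the visit.** The injection day is Day 1 (SAP 8.1.9.2), and the Day 8 window is ±1 (both schedules). For a visit on day v, days elapsed since injection = v − 1. Full diary days among Days 1–7 = min(7, v − 1). If the window runs to Day 8, full days = min(8, v − 1).

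| Visit on | Days since injection | Full days of Days 1–7 | Full days of Days 1–8 |
|---|---|---|---|
| Day 7 | 6 | 6 | 6 |
| Day 8 | 7 | 7 | 7 |
| Day 9 | 8 | 7 | 8 |

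A Day 7 visit leaves six full days plus part of Day 7. The decision on whether events persist at 7 days is then also made at 6 days.

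**2. What can be lost.** Three conditions must hold together: the visit is on Day 7; nothing is unresolved at the visit, so no second diary week starts; and the event begins after the visit, or has already resolved and was neither entered nor mentioned.

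**3. Whether Day 15 recovers it.** SAP 8.1.9.2 defines solicited events as those recorded in the diary with a grade given by the participant. SAP 8.1.9.1 keeps solicited events out of the unsolicited tables unless onset is more than 7 days after vaccination or the event is serious or medically attended. A mild Day 7 event first mentioned at Day 15 has no clear place in either set of tables.

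**4. Size, on assumed inputs.** Let f be the share of subjects seen on Day 7, p the true Day 7 rate, and q the share of Day 7 events meeting the other two conditions in step 2. If a blank day counts as no event, understatement = f × p × q and reported rate = p × (1 − f × q).

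- f = 0.10, p = 5%, q = 0.25: 0.125 points lost, 4.875% reported.
- f = 1/3, p = 5%, q = 0.25: 0.42 points lost, 4.58% reported.
- f = 0.5, p = 10%, q = 0.5: 2.5 points lost, 7.5% reported.
- q = 0: nothing lost.

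The one-third value is what visits spread evenly over Days 7 to 9 would give. The incidence at any time from Day 1 to Day 7 loses a subject for a given term only if that subject's first such event falls in the unrecorded part of Day 7.

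**5. A separate mismatch.** Under the study-day formula in SAP 5.3.2, the date 7 days after injection is study Day 7 + 1 = Day 8. Table (i) can therefore reach Day 8, while table (ii) stops at Day 7. On the longer reading, even an on-time Day 8 visit collects the diary before its last day has ended (second row of the table).

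**The case against.** A reader might infer that the diary cannot be complete for anyone seen on Day 7, and that Day 7 rates are therefore understated. The documents do not support either statement.

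- A once-daily Day 7 entry can be made before or at the visit, and staff ask about each solicited term there. Events ongoing at the visit are seen, and they keep the diary running to Day 15.
- No section says that a blank day counts as no event. Not imputing missing data does not make a blank a negative. The cohort-total denominator in SAP 8.1.9.1 is written for the unsolicited tables. If the by-day denominator were subjects with an entry, the direction of any bias would not be fixed.
- It is also tempting to say that two of eight onset days are lost. The Day 8 part comes from the mismatch between tables (i) and (ii), not from the early visit.

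Two further defences are weaker. Footnote 7 names Day 8, but that is the label of a visit with a window. Completion status in 6.2.1 could be read as a check that seven days are filled in. Read with the rest of 6.2.1 and footnote 7, however, it separates subjects who are doing a second week from those who are not.

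The scale argument also has force. Analyses are descriptive, and subjects are told to contact the site immediately about solicited events of grade 3 or above, so a severe late onset is unlikely to pass unnoticed. What remains is that the printed rules permit early collection and nothing in them prevents the loss of a milder late onset.

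**Conclusion.** The point holds in a limited form. A compliant Day 7 visit can end diary recording before the required seven days are over, so the record behind the primary reactogenicity endpoint is not guaranteed complete for subjects seen that day who do not go on to a second week. At most part of one day in Days 1–7 is at risk, and only under the conditions in step 2.

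Day 7 rates may be slightly understated if blank days are treated as no event. The illustrations run from zero to 2.5 percentage points and rest wholly on assumed f, p and q. The effect on Day 1–7 incidence at any time is probably small. This does not threaten the overall safety conclusion, but it is worth correcting because the printed rules themselves cause the gap and the remedy is cheap.

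**What to change.** 1. In Protocol 6.2.1 and Appendix 1 footnote 7, state that the diary is not collected until the 7-day recording period is complete. If the visit falls earlier, review the diary then, leave it with the subject, and collect it at the scheduled Day 15 visit.
2. In SAP 8.1.9.2 (ii), use subjects with a diary entry for that day as the by-day denominator, show that number, and state how days without an entry are handled. This works best together with item 1. Alone, it could drop mainly symptom-free subjects from the Day 7 row.
3. Separately, reconcile the onset windows of tables (i) and (ii). Removing the negative visit window would protect Days 1–7 but would not secure Day 8 if table (i) is meant to include it.

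The cost is one sentence in the Protocol and short additions to the SAP. No visit is added, because Day 15 already carries a diary review. The downside is that a few diaries come back a week later. If diaries have already been collected, the sponsor can still count Day 7 visits from the recorded dates and put items 2 and 3 into the plan for the final analysis.

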APPENDIX 2: LIST OF LABORATORY ANALYTES

Appendix 2: List of Laboratory Analytes

Clinical Chemistry Panel	Hematology	Urine Dipstick Analysis	Immunogenicity
• Sodium	• Red blood cells	• Color	• SARS CoV-2 neutralising antibody titer by PRNT and/or pseudovirus neutralization test and/or sVNT and/or microneutralization test
• Potassium	• Hemoglobin	• Appearance	• Anti-S full length protein and anti-RBD IgG
• Chloride	• Hematocrit	• Specific gravity	• T-cell surface markers (CD3, CD4, CD8, CD45RA, CCR7)
• Bicarbonate	• MCV, MCH, MCHC	• pH	T-cell intracellular cytokines (IFN- γ , IL-2, TNF α , IL-4)
• Total protein	• Platelets	• Protein	
• Albumin	• White blood cells	• Blood	
• Calcium	• WBC Differential (%) and absolute)	• Ketones	
• Magnesium	• Neutrophils	• Urobilinogen	
• Phosphorus	• Eosinophils	• Glucose	
• Glucose (random)	• Basophils	• Bilirubin	
• BUN	• Lymphocytes	• Leukocyte esterase	
• Creatinine	• Monocytes	• Nitrite	
• Cholesterol		• Microscopic examination ¹	
• Uric Acid			
• Total bilirubin	Coagulation Panel	Urine Laboratory Analysis	
• Direct (conjugated) bilirubin	• aPTT	• UPCR	
• Indirect (unconjugated) bilirubin	• PT		
• ALT	• INR		
• AST			
• Alkaline phosphatase			
• Creatinine kinase			
• GGT			
	Other Screening Tests		SARS-CoV-2 Confirmation
	• Serum β hCG		• PCR ²
	• Drug/Alcohol screen		• Anti-nucleocapsid antibody ^{2, 3}
	• HbA1c		

1 Will be performed on abnormal findings unless otherwise specified

2 May be performed in local lab

3 May be performed on retained serum samples if required to confirm SARS-CoV-2 infection

APPENDIX 3: LIST OF EXCLUSIONARY AUTOIMMUNE DISEASES

Appendix 3: List of Exclusionary Autoimmune Diseases

The following list details the autoimmune diseases listed by the American Autoimmune Related Disease Association (<https://www.aarda.org/diseaselists>). These autoimmune diseases represent exclusion criteria for the purpose of eligibility to participate in this study.

- Achalasia
- Addison's disease
- Adult Still's disease
- Agammaglobulinemia
- Alopecia areata
- Amyloidosis
- Ankylosing spondylitis
- Anti-GBM/Anti-TBM nephritis
- Antiphospholipid syndrome
- Autoimmune angioedema
- Autoimmune dysautonomia
- Autoimmune encephalomyelitis
- Autoimmune hepatitis
- Autoimmune inner ear disease (AIED)
- Autoimmune myocarditis
- Autoimmune ophoritis
- Autoimmune orchitis
- Autoimmune pancreatitis
- Autoimmune retinopathy
- Autoimmune urticaria
- Axonal & neuronal neuropathy (AMAN)
- Baló disease
- Behcet's disease
- Benign mucosal pemphigoid
- Bullous pemphigoid
- Castleman disease (CD)
- Celiac disease
- Chagas disease
- Chronic inflammatory demyelinating polyneuropathy (CIDP)
- Chronic recurrent multifocal osteomyelitis (CRMO)
- Churg-Strauss Syndrome (CSS) or Eosinophilic Granulomatosis (EGPA)
- Cicatricial pemphigoid
- Cogan's syndrome
- Cold agglutinin disease
- Congenital heart block
- Coxsackie myocarditis
- CREST syndrome
- Crohn's disease
- Dermatitis herpetiformis

- Dermatomyositis
- Devic's disease (neuromyelitis optica)
- Discoid lupus
- Dressler's syndrome
- Endometriosis
- Eosinophilic esophagitis (EoE)
- Eosinophilic fasciitis
- Erythema nodosum
- Essential mixed cryoglobulinemia
- Evans syndrome
- Fibromyalgia
- Fibrosing alveolitis
- Giant cell arteritis (temporal arteritis)
- Giant cell myocarditis
- Glomerulonephritis
- Goodpasture's syndrome
- Granulomatosis with Polyangiitis
- Graves' disease
- Guillain-Barre syndrome
- Hashimoto's thyroiditis
- Hemolytic anemia
- Henoch-Schonlein purpura (HSP)
- Herpes gestationis or pemphigoid gestationis (PG)
- Hidradenitis Suppurativa (HS) (Acne Inversa)
- Hypogammaglobulinemia
- IgA Nephropathy
- IgG4-related sclerosing disease
- Immune thrombocytopenic purpura (ITP)
- Inclusion body myositis (IBM)
- Interstitial cystitis (IC)
- Juvenile arthritis
- Juvenile diabetes (Type 1 diabetes)
- Juvenile myositis (JM)
- Kawasaki disease
- Lambert-Eaton syndrome
- Leukocytoclastic vasculitis
- Lichen planus
- Lichen sclerosus
- Ligneous conjunctivitis
- Linear IgA disease (LAD)
- Lupus
- Lyme disease chronic
- Meniere's disease

- Microscopic polyangiitis (MPA)
- Mixed connective tissue disease (MCTD)
- Mooren's ulcer
- Mucha-Habermann disease
- Multifocal Motor Neuropathy (MMN) or MMNCB
- Multiple sclerosis
- Myasthenia gravis
- Myositis
- Narcolepsy
- Neonatal Lupus
- Neuromyelitis optica
- Neutropenia
- Ocular cicatricial pemphigoid
- Optic neuritis
- Palindromic rheumatism (PR)
- PANDAS
- Paraneoplastic cerebellar degeneration (PCD)
- Paroxysmal nocturnal hemoglobinuria (PNH)
- Parry Romberg syndrome
- Pars planitis (peripheral uveitis)
- Parsonage-Turner syndrome
- Pemphigus
- Peripheral neuropathy
- Perivenous encephalomyelitis
- Pernicious anemia (PA)
- POEMS syndrome
- Polyarteritis nodosa
- Polyglandular syndromes type I, II, III
- Polymyalgia rheumatica
- Polymyositis
- Postmyocardial infarction syndrome
- Postpericardiotomy syndrome
- Primary biliary cirrhosis
- Primary sclerosing cholangitis
- Progesterone dermatitis
- Psoriasis
- Psoriatic arthritis
- Pure red cell aplasia (PRCA)
- Pyoderma gangrenosum
- Raynaud's phenomenon
- Reactive Arthritis
- Reflex sympathetic dystrophy
- Relapsing polychondritis

- Restless legs syndrome (RLS)
- Retroperitoneal fibrosis
- Rheumatic fever
- Rheumatoid arthritis
- Sarcoidosis
- Schmidt syndrome
- Scleritis
- Scleroderma
- Sjögren's syndrome
- Sperm & testicular autoimmunity
- Stiff person syndrome (SPS)
- Subacute bacterial endocarditis (SBE)
- Susac's syndrome
- Sympathetic ophthalmia (SO)
- Takayasu's arteritis
- Temporal arteritis/Giant cell arteritis
- Thrombocytopenic purpura (TTP)
- Thyroid eye disease (TED)
- Tolosa-Hunt syndrome (THS)
- Transverse myelitis
- Type 1 diabetes
- Ulcerative colitis (UC)
- Undifferentiated connective tissue disease (UCTD)
- Uveitis
- Vasculitis
- Vitiligo
- Vogt-Koyanagi-Harada Disease

